11. SAMPLE SIZE JUSTIFICATION

A previous study (7) with a design essentially identical to the present study demonstrated highly significant differences between treatment groups for achievement of complete debridement (85% vs. 29%, P<0.003), reduction in % area of non-viable tissue for each week (P<0.002), and in reduction in wound area (P<0.009). The sample size of this previous trial was 27 subjects, 13 in the SANTYL group, and 14 in the hydrogel group. Based on the reported outcomes in the previous trial, 26 subjects are required to detect a difference in the primary endpoint: the proportion of ulcers achieving complete debridement during the 6-week treatment period. This relates to a Fisher's Exact test assuming 85% vs 29% in the proportion of ulcers achieving complete debridement. To allow for 15% drop-out rate throughout the 6-week treatment period, a total of 32 subjects will be randomized (16 per treatment) in an equal allocation ratio for SANTYL and hydrogel. In the previous studies quoted, the secondary endpoints including reduction in % area of non-viable tissue and reduction in wound area were found to reach significance with similar numbers.

12. ADVERSE EVENTS

12.1 GENERAL INFORMATION

An AE is any untoward medical occurrence in a patient administered a medicinal product and which does not necessarily have to have a causal relationship with this treatment. An AE can therefore be any unfavorable and unintended sign (for example, an abnormal laboratory finding), symptom, or disease temporally associated with the use of a medicinal product, whether or not considered related to this medicinal product.

Adverse drug reactions (ADR) are noxious and unintended responses to a medicinal product, meaning that a causal relationship between a medicinal product and an AE is at least a reasonable possibility. A reaction, in contrast to an event, is characterized by the fact that a causal relationship between the drug and the occurrence is suspected.

12.2 Non-serious Adverse Events

A non-serious AE is defined as a change from baseline (pre-treatment) in a subject's medical health that is not life-threatening, does not require hospitalization, does not prolong a current hospitalization, and is not disabling. Non-serious AE must be reported to Smith & Nephew by use of an Adverse Event Form. All non-serious AE must be reported in the subject's source documents: AE associated with the target ulcer must be recorded on an Adverse Event Form in the source and eCRF regardless of whether or not they are considered to be related to the test article. AE related to the test article must also be recorded on an Adverse Event Form in the source and eCRF.

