7.2 INCLUSION CRITERIA

Subjects will be considered qualified for enrollment if they meet the following criteria:

- Provide written informed consent, which will consist of reading, signing, and dating the informed consent document after the Investigator, sub-Investigator or other designated study staff member has explained the study procedures, risks, and contact information.
- 2. Eighteen years of age or older, of either sex, and of any race.

- 3. Willing to comply with protocol instructions, including allowing all study assessments.
- 4. Subject is in-patient in a long-term care facility.
- A pressure ulcer present with a surface area ≥ 1.0 cm² and ≤ 64.0 cm² confirmed using the ImageIQ EDCIQ mobile imaging system. Only one qualifying ulcer per subject will be selected for the study (selection based on greatest clinical need, as assessed by the Investigator).
- The target ulcer must present with ≥85% necrotic, nonviable tissue as assessed by at least one independent image reviewer.
- The target ulcer has not been previously treated with hydrogel (SoloSite[®]) or with SANTYL. Prior ulcers at or near the same location may have been treated with these products.
- No current infections requiring treatment with antibiotics (antibiotic use is permitted for the purpose of urinary tract infection prophylaxis, but this must be explicitly stated in the subject's chart).
- Acceptable state of health and nutrition with pre-albumin levels of ≥ 10 mg/dL (0.10 g/L), per the Screening local lab report. This is not required if a pre-albumin test within range has been conducted within the last 30 days.
- A hemoglobin A1c < 7.9% per the Screening local lab report. This is not required if a hemoglobin A1c test within range has been conducted within the last 30 days.

- Have adequate pressure redistribution to the affected area or off-loading if the ulcer is on a lower extremity.
- 12. No known allergies or sensitivities to either test article or the dressings.
- 13. Women of child-bearing potential (those who are not premenarchal, not surgically sterilized [hysterectomy or bilateral oophorectomy], or not post-menopausal), may participate in the study if they meet the following condition:
 - A negative urine pregnancy test at screening

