12.3 SERIOUS ADVERSE EVENTS

A serious adverse event (SAE) or reaction is any untoward medical occurrence that at any dose:

- Results in death
- Is life-threatening (NOTE: The term "life-threatening" in the definition of "serious" refers
 to an event/reaction in which the patient was at risk of death at the time of the

event/reaction; it does not refer to an event/ reaction which hypothetically might have caused death if it were more severe)

- · Requires inpatient hospitalization or results in prolongation of existing hospitalization
- · Results in persistent or significant disability/incapacity
- · Is a congenital anomaly/birth defect
- · Is a medically-important event or reaction

Medical and scientific judgment should be exercised in deciding whether other situations should be considered scrious such as important medical events that might not be immediately life-threatening or result in death or hospitalization but might jeopardize the patient or might require intervention to prevent one of the other outcomes listed in the definition above. Examples of such events are intensive treatment in an emergency room or at home for allergic bronchospasm, blood dyscrasias, or convulsions that do not result in hospitalization; or development of drug dependency or drug abuse.

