12.4 REPORTING OF AE AND SAE

AE associated with the target ulcer and all SAE of any kind will be recorded in the AE eCRF. For each recorded event, the eCRF must include the event's onset and resolution date (if the event has resolved), the frequency and severity of the event, a summary of any action taken as a result of the event (both in regard to any treatment given and to any change in dosing with the test article), and an assessment of the event's relationship to the test article. AE judged to be related to the test article and all SAE will be entered into the eCRF and reported to the Sponsor within 24 hours of knowing about the event. Target ulcer AE judged not related to the test article will be entered into the safety database within 48 hours of the site becoming aware of the event. All SAE and test article-related AE will be reviewed by the Medical Monitor and the Medical Reviewer to determine which, if any, meet expedited reporting criteria. All events requiring expedited reporting will be forwarded to Regulatory by the Medical Reviewer for further processing.

A Serious Adverse Event Form must be completed for all SAE and forwarded to Smith & Nephew within 24 hours of the Investigator's knowledge of the event and to the Institutional Review Board/Independent Ethics Committee, according to their requirements. When new significant information is obtained as well as when the outcome of an event is known, the Investigator must provide Smith & Nephew with this information as soon as it becomes available. Depending on the nature of the AE, Smith & Nephew may request copies of the subject's medical records as well as results of any relevant laboratory tests performed. If the subject was hospitalized, a copy of the discharge summary may be requested by Smith & Nephew and should be forwarded as soon as it becomes available. In certain cases, Smith & Nephew also may request a letter from the Investigator that summarizes the events related to the case.

SAE must be reported using the eCRF system (preferred), or via telephone or fax, to one of the following Smith & Nephew representatives within 24 hours of the Investigator's knowledge of the event:

Table 12.4-1: Study Contact Information

[name]	Business [contact]	
Medical Monitor	Business [contact]	
	Mobile [contact]	
[name], MPH	Business [contact]	
Medical Reviewer	Business [contact]	
	Mobile [contact]	

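### Section 12.2 omits the medically important ground used in Section 12.3, so one adverse event can meet both the non-serious and the serious definition

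*Combined protocol and SAP*

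**What the plan says.** Section 12.2 opens: "A non-serious AE is defined as a change from baseline (pre-treatment) in a subject's medical health". It then attaches four conditions: "that is not life-threatening, does not require hospitalization, does not prolong a current hospitalization, and is not disabling". It does not refer to Section 12.3.

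Section 12.3 lists six grounds, any one of which makes an event serious. The last is "Is a medically-important event or reaction". The paragraph below the list explains that this covers "important medical events that might not be immediately life-threatening or result in death or hospitalization but might jeopardize the patient". Its examples include convulsions or bronchospasm treated intensively in an emergency room or at home without admission.

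Section 12.4 sets the reporting routes:

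- On 24-hour notice: "AE judged to be related to the test article and all SAE will be entered into the eCRF and reported to the Sponsor". The 24-hour limit follows in the same sentence.
- Review by the Medical Monitor and Medical Reviewer for expedited reporting covers the same two groups, SAEs and related AEs.
- The SAE form, which also goes to the IRB/IEC, is required for SAEs only.
- For the remaining ulcer events: "Target ulcer AE judged not related to the test article will be entered into the safety database within 48 hours".

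Section 12.2 adds that non-serious AEs go to the sponsor on an Adverse Event Form and into the source documents. It sets no time limit.

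**The concern.** The two definitions should be complements, with every AE falling under exactly one. As written they overlap. An event that is important but does not threaten life at once, lead to hospitalization or disable the subject satisfies every condition in 12.2 and also satisfies 12.3.

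The classification decides which safety steps follow. The SAE form and IRB/IEC report depend on seriousness alone. Sponsor notice within 24 hours and medical review depend on seriousness or relatedness. For an event judged not related, seriousness is therefore the only route to any of the four. Section 12.5 makes the not-related class fairly wide: it includes events considered unlikely to be related, and it asks for additional evidence before an event common in this population is called possibly related.

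**Working it through.** No arithmetic applies, and the plan gives no figure to reproduce. The check has two parts.

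**1. Each 12.3 ground against the 12.2 conditions**

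| Ground in 12.3 | Ruled out of non-serious by 12.2? |
|---|---|
| Death | Not named, but a fatal event would ordinarily fail the condition of not being life-threatening |
| Life-threatening | Yes |
| Hospitalization or its prolongation | Yes, by two of the four conditions |
| Disability | Yes |
| Congenital anomaly | Not named, but 12.2 covers only a change in the subject's own health, which an anomaly in offspring does not clearly meet |
| Medically important | No |

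Only the medically important ground produces a clear overlap. Take one of 12.3's own examples, a convulsion treated in an emergency room without admission, and assume no immediate threat to life and no disability. It passes all four conditions in 12.2 and is serious under 12.3.

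**2. What happens if that event is filed as non-serious (12.2 and 12.4)**

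| Event | SAE form | IRB/IEC report | 24-hour notice | Medical review | What remains |
|---|---|---|---|---|---|
| Related to test article | Lost | Lost | Kept | Kept | Adverse Event Form, eCRF |
| Not related, target ulcer | Lost | Lost | Lost | Lost | Adverse Event Form, eCRF, database entry within 48 hours |
| Not related, elsewhere | Lost | Lost | Lost | Lost | Adverse Event Form and source documents, no time limit in 12.2 |

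Two of the four steps are lost whatever the relatedness. All four are lost only when the event is judged not related.

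**The case against.** The strongest reply is that the operative rule is complete. Section 12.3 lists all six grounds and gives a paragraph with examples to the very events at issue. Section 12.4 applies to SAEs of any kind, and Appendix 18.3 (item 9) requires 24-hour reporting of every SAE, related or not. Nothing lets 12.2 displace these, and coming first in the text is not a rule of precedence. Harm requires someone to stop at 12.2 and not apply the next section. The sponsor also receives an Adverse Event Form and could question the classification.

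Most of this stands and limits the point to an ambiguity. It does not remove the point. Sections 12.4 and 18.3 bind events already classed as SAEs, and the conflict lies in the classification. The Adverse Event Form carries no deadline in 12.2, and 12.4 assigns medical review only to SAEs and related AEs.

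A reader might go further in four ways that the documents do not support:

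- **Birth defects also fall between the definitions.** Section 12.2 is limited to the subject's own health, and Section 9.3 gives pregnancy a separate route. Counting the grounds missing from 12.2 is also unhelpful: three are unnamed if read literally, but only one is clearly missed in substance.
- **SAE counts by arm will be distorted.** There is one center, no differential effect by arm is shown, and Section 10.4 names no table of SAEs by arm.
- **The overlap is likely in this population.** No event rate is given, so its frequency cannot be bounded.
- **Hospitalization has no meaning here because every subject is already a long-term-care in-patient** (criterion 4 in Section 7.2: "Subject is in-patient in a long-term care facility"). That is too strong. Section 12.4 mentions a discharge summary if the subject was hospitalized, which treats hospitalization as something other than residence. How the term applies is a separate question for clarification.

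**Conclusion.** The inconsistency is real and narrow. Section 12.2 is not the complement of 12.3, and a medically important event managed without hospitalization fits both. Misfiling it under 12.2 costs the SAE form and the IRB/IEC report in every case. If the event is judged not related, it also costs the 24-hour notice and the medical review.

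This rests on two conditions: that the event meets none of the four exclusions in 12.2, and that the person classifying it applies 12.2 without carrying 12.3 through. How often both would hold cannot be estimated from the documents. The text permits misclassification and does not direct it. No efficacy analysis, sample size or eligibility rule is touched. It merits correction because it affects safety routing and is easy to remove.

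**What to change.** Replace the definition in Section 12.2 with a cross-reference: a non-serious AE is any AE that meets none of the seriousness criteria in Section 12.3. This makes the definitions complementary for all six grounds and needs no separate precedence rule. Carry the same wording into the eCRF completion guidelines.

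Separately, ask the sponsor to state how hospitalization, and its prolongation, apply to subjects who already live in long-term care. This review does not propose the rule, since some definitions could narrow SAE capture.

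The cost is one sentence in the protocol and a matching line in the guidelines. A few more events may be reported as SAEs. Design, treatment and analysis are unchanged.

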12.3 SERIOUS ADVERSE EVENTS

A serious adverse event (SAE) or reaction is any untoward medical occurrence that at any dose:

- Results in death
- Is life-threatening (NOTE: The term "life-threatening" in the definition of "serious" refers
 to an event/reaction in which the patient was at risk of death at the time of the

event/reaction; it does not refer to an event/ reaction which hypothetically might have caused death if it were more severe)

- · Requires inpatient hospitalization or results in prolongation of existing hospitalization
- · Results in persistent or significant disability/incapacity
- · Is a congenital anomaly/birth defect
- · Is a medically-important event or reaction

Medical and scientific judgment should be exercised in deciding whether other situations should be considered scrious such as important medical events that might not be immediately life-threatening or result in death or hospitalization but might jeopardize the patient or might require intervention to prevent one of the other outcomes listed in the definition above. Examples of such events are intensive treatment in an emergency room or at home for allergic bronchospasm, blood dyscrasias, or convulsions that do not result in hospitalization; or development of drug dependency or drug abuse.

12.4 REPORTING OF AE AND SAE

AE associated with the target ulcer and all SAE of any kind will be recorded in the AE eCRF. For each recorded event, the eCRF must include the event's onset and resolution date (if the event has resolved), the frequency and severity of the event, a summary of any action taken as a result of the event (both in regard to any treatment given and to any change in dosing with the test article), and an assessment of the event's relationship to the test article. AE judged to be related to the test article and all SAE will be entered into the eCRF and reported to the Sponsor within 24 hours of knowing about the event. Target ulcer AE judged not related to the test article will be entered into the safety database within 48 hours of the site becoming aware of the event. All SAE and test article-related AE will be reviewed by the Medical Monitor and the Medical Reviewer to determine which, if any, meet expedited reporting criteria. All events requiring expedited reporting will be forwarded to Regulatory by the Medical Reviewer for further processing.

A Serious Adverse Event Form must be completed for all SAE and forwarded to Smith & Nephew within 24 hours of the Investigator's knowledge of the event and to the Institutional Review Board/Independent Ethics Committee, according to their requirements. When new significant information is obtained as well as when the outcome of an event is known, the Investigator must provide Smith & Nephew with this information as soon as it becomes available. Depending on the nature of the AE, Smith & Nephew may request copies of the subject's medical records as well as results of any relevant laboratory tests performed. If the subject was hospitalized, a copy of the discharge summary may be requested by Smith & Nephew and should be forwarded as soon as it becomes available. In certain cases, Smith & Nephew also may request a letter from the Investigator that summarizes the events related to the case.

SAE must be reported using the eCRF system (preferred), or via telephone or fax, to one of the following Smith & Nephew representatives within 24 hours of the Investigator's knowledge of the event:

Table 12.4-1: Study Contact Information

[name]	Business [contact]	
Medical Monitor	Business [contact]	
	Mobile [contact]	
[name], MPH	Business [contact]	
Medical Reviewer	Business [contact]	
	Mobile [contact]	

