9.1 VISITS AND EXAMINATIONS

9.1.1 Screening Visit (SCR)

NOTE: Any subject who signs an informed consent, but fails to meet the required entry criteria is considered to be a Screen Failure. Their demographic information must be captured in the Eligibility CRF with the reason for screen failure specified.

Explain the purpose and nature of the study, and have the subject or the subject's legally-authorized representative read, sign, and date the IRB-approved informed consent document. In addition, the informed consent document must be signed and dated by the individual who consents the subject. Provide a photocopy of the signed informed consent document to the subject or subject representative, and place the original signed document in the subject's medical record.

--- Do not proceed until consent has been obtained ---

- Assign a subject ID number (format xx-yyy, where xx=01, the two-digit site number, and yyy=three-digit sequential subject number).
- Obtain demographic information and medical history, including information on all concomitant medications.
- Photograph the target ulcer using the ImageIQ EDCIQ mobile imaging system (refer to Section 9.4.1).
 - Target ulcer area must be between 1.0 cm² and 64.0 cm² (inclusive) and have at least 85% of the surface covered with necrotic, nonviable tissue as assessed by at least one independent image reviewer.
- If the ulcer is on a lower extremity, obtain ABI for the target ulcer limb. ABI must not be less than 0.85.

- Screen the subject for protocol inclusion and exclusion criteria. If the subject does not
 meet ALL inclusion criteria or does meet ANY exclusion criterion, the subject must be
 dismissed as a screen failure.
- Obtain a venous blood sample for serum pre-albumin and hemoglobin A1c measurements (send blood to local laboratory for analysis).
 - **Note**: If an HbA1c or pre-albumin test has been conducted within the last 30 days and is recorded in the subject's chart, an additional test is not required.
- 8. Conduct a urine pregnancy test for women of childbearing potential.
- If any adverse events are observed or reported due to study-mandated procedures (e.g., venous blood sample), the events must be reported as instructed in Section 12, Adverse Events.
- 10. Study Visit I should be scheduled within 7 days of the Screening Visit.

9.1.2 Randomization/Study Visit 1

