10.4 SAFETY

Safety variables include adverse events (AE), AE will be coded using the Medical Dictionary for Regulatory Activities (MedDRA). The treatment-emergent AEs will be reported separately for the 6-week treatment period (Study Visits 2 to 7) and initial screening period (interval between Screening Visit 1 and Screening Visit 2). Frequency of treatment-emergent AE will be calculated for each body system, by preferred term, by subject group (i.e., SANTYL, hydrogel), for number of subjects and proportion reporting the event for the safety population. The severity of the AE and the relationship to study medication will be summarized for each body system and preferred term by subject group. Withdrawals in general and withdrawals due to AE will be summarized for each body system and preferred term by subject group.

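### Sections 12.2 and 12.4 route only target-ulcer, related and serious AEs to the eCRF, other wording points to full capture, and 10.4 tabulates AEs by arm with no such limit

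*Combined protocol and SAP*

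**What the plan says.** Section 12.2 deals with non-serious events. Straight after the definition it sets a general duty: "Non-serious AE must be reported to Smith & Nephew by use of an Adverse Event Form". It then requires every non-serious AE to be in the source documents and names the eCRF for two kinds. The first is ulcer events: "AE associated with the target ulcer must be recorded on an Adverse Event Form in the source and eCRF regardless of whether" (the sentence ends by setting causality aside). The second is related events: "AE related to the test article must also be recorded on an Adverse Event Form in the source and eCRF".

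Section 12.4 follows the same pattern: "AE associated with the target ulcer and all SAE of any kind will be recorded in the AE eCRF". Related AEs and all SAEs have a 24-hour timeline. Unrelated AEs have a 48-hour timeline, but only if they concern the target ulcer.

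Section 12.5 gives the causality decision to the Principal Investigator. Section 8.2 explains that the products look different and the study medication cannot be double-blinded; the blinded assessors work from photographs.

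Section 10.4 sets out the analysis: "Frequency of treatment-emergent AE will be calculated for each body system, by preferred term, by subject group", in the safety population. It adds severity and relationship to study medication by body system, preferred term and arm, and "Withdrawals in general and withdrawals due to AE will be summarized for each body system and preferred term by subject group". It reports the treatment period "and initial screening period" separately. Nothing in it limits the tables to ulcer-associated, related or serious events.

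**The concern.** The collection rules and the analysis rules do not describe the same set of events. For a non-serious event away from the ulcer, the only AE-specific route into the eCRF is a judgement that the product may have caused it, made by someone who can know which product was applied. If the tables in 10.4 rest on those records, their counts for such events mix how often the events happen with how often they are attributed to treatment. A difference between arms in attribution could then look like a difference in safety, and a real difference in events judged unrelated would not appear. A reader of a table by body system and arm would normally take it to show all treatment-emergent AEs and would have no warning otherwise.

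**Working it through.** No figure in the plan bears on this and no arithmetic applies. The check sets the sections side by side.

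**Step 1. eCRF route by type of event, using the AE-specific sentences of 12.2 and 12.4.**

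| Type of event | Route to the AE eCRF | Within 10.4 if treatment-emergent |
|---|---|---|
| Serious, any site, any causality | Yes (12.4) | Yes |
| Non-serious, target ulcer, any causality | Yes (12.2, 12.4) | Yes |
| Non-serious, not target ulcer, judged related | Yes (12.2, 12.4) | Yes |
| Non-serious, not target ulcer, judged not related | None stated | Yes |

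Only the last row is at issue. Section 12.2 still puts those events in the source documents.

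**Step 2. What separates the last two rows.** The only difference is the causality call. Under 12.5 an event that is common in this population needs further evidence before it counts as possibly related, so common long-term-care events tend to fall in the last row.

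**Step 3. Wording that points the other way.**
- The general reporting sentence of 12.2 has no limit. It concerns reporting to the sponsor on a form and does not mention the eCRF.
- Section 9.1.3 requires every AE in the treatment period to be recorded. It does not say where, and its procedure step refers to Section 12.
- Section 18.3, item 11b, has the investigator move source data to the appropriate case report forms. This is a general duty and not specific to AEs.
- Section 18.3, item 9, has all AEs reported to the sponsor as the protocol specifies, which leads back to Section 12.

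These support full capture, while the sentences that name the AE eCRF select. A site could follow either and believe it complied.

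**Step 4. Effect on 10.4 if the eCRF sentences are followed and the tables are built from the eCRF.**
- The frequency tables omit the last row.
- In the relationship summary, the not-related category for non-serious events away from the ulcer is empty by construction.
- A withdrawal due to such an event has no AE eCRF record from which to take the body system and preferred term.

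**Step 5. An illustration.** Section 9.1.1 covers the case where "adverse events are observed or reported due to study-mandated procedures", such as the blood draw, and refers to Section 12. No test article has been applied by then. The eCRF sentences would leave such a non-serious event in source; the general sentence of 12.2 would send it to the sponsor. The same event is handled in two ways, depending on which sentence is read.

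**The case against.** The strongest reply is that nothing is lost. All non-serious AEs are in source, item 11b of 18.3 moves source data to case report forms, and the general sentence of 12.2 sends non-serious AEs to the sponsor, which under Section 10 also does the data management and analysis. Section 12.4 mentions a safety database, and 10.4 does not say that its tables come from the eCRF alone. The sentences of 12.2 could also be reconciled: one sets the duty to report to the sponsor, and the others say which forms must also be in the eCRF. Much of this stands. It rules out saying that these events are recorded nowhere or never reach the sponsor. It does not say which records feed the tables, and it leaves the AE-specific eCRF sentences narrower than 10.4.

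A second reply is that limiting eCRF entry to serious, local and related events is a reasonable choice in a Phase 4 topical study. That is fair, but then 10.4 should say so.

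A third is that the formal SAP to which Section 10 defers, or the CRF completion guidelines mentioned in 18.3, may settle the scope. Neither is in the supplied text, so this cannot be checked. The protocol's own instructions would still conflict.

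**Conclusion.** The point holds as a conflict between stated rules. The AE-specific eCRF sentences cover less than 10.4 tabulates, and the general wording pulls towards full capture. The consequence is conditional: it arises if the site follows the eCRF sentences and the tables are built from the eCRF. Non-serious non-ulcer events would then be counted only when an unmasked investigator calls them related.

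The size cannot be estimated. The documents give no AE rate and no expected share judged related, so any count of missing events would rest on assumed inputs.

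A reader might infer two stronger conclusions, and the documents support neither:
- *That the safety comparison is biased between arms.* The text creates an opening for this but gives no evidence that calls would differ by arm, and 10.4 plans descriptive summaries with no between-arm test.
- *That no non-ulcer event from screening would be captured.* That depends on one contested reading, since the general sentence of 12.2 is also part of Section 12. Those events also precede randomization, so they cannot distort a comparison of arms.

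Efficacy is unaffected, and SAEs and target-ulcer AEs are captured whatever their causality. This is a minor point, worth correcting because the correction is cheap.

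**What to change.** Amend 12.2 and the first sentence of 12.4 to one rule, for example: *every AE from informed consent to exit, serious or not, at the target ulcer or elsewhere, and whatever the causality assessment, is entered on an Adverse Event Form in source and in the AE eCRF.* Keep the 24-hour and 48-hour timelines, and give the remaining events a looser one, such as the next weekly visit.

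The cost is modest: data entry, MedDRA coding and source checks for events already held in source, in a study of about 32 randomized subjects. Nothing more is asked of subjects. The tables will also carry common long-term-care events with little bearing on the products.

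If the sponsor intends selective collection, state in 10.4 and in the table titles that the AE tables cover only SAEs, target-ulcer AEs and test article-related AEs. That costs a sentence and makes the tables honest, but it keeps the selection by causality call, so full capture is preferable.
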